### 7.5.2.4 Analysis of Time to First IPF Exacerbation or Death

Time to first IPF exacerbation or death is defined as the time from start of study treatment to first acute exacerbation of IPF which is determined by the investigator (Adverse event CRF, AE preferred term equal to Idiopathic pulmonary fibrosis) or death for each subject. Subjects who do not experience acute exacerbation of IPF will be censored to the last known alive date.

The analysis of time to first IPF exacerbation or death of each active treatment arm versus placebo will be performed using a log-rank test stratified with standard of care to generate p-value for each comparison. Median time to first IPF exacerbation and corresponding 95% CI as well as proportion of subjects without the event at 8-week interval will be summarized for each treatment arm using the Kaplan-Meier (KM) analysis. KM plot of time to first IPF exacerbation will also be presented by treatment. In addition, the hazard ratio and 95% CI will be calculated from a stratified Cox proportional hazards model that includes standard of care as the strata.

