### 7.5.2.5 Other Secondary Analyses

The rates of hospitalization for respiratory ailments, which is defined as the number of patients with any hospitalization for respiratory ailments divided by the total study duration (years) summed over patients in that treatment arm and then multiplied by 100 to present in terms of per 100 patient years, will be tabulated by treatment arm. Tests of differences in event rate will be assessed using chi-squared tests ( $\chi^2$ ) at the 2-sided, 0.05 level of significance. Corresponding exact 95% CIs of study treatment proportions and respective active ND-L02-s0201 differences from placebo will be estimated. Time to hospitalization for respiratory ailments or death is defined as the time from start of study treatment to hospitalization for respiratory ailments or death for each subject. Subjects who do not experience hospitalization for respiratory ailments and have not died will be censored to last known alive date. The analysis of time to hospitalization for respiratory ailments or death of each active treatment arm versus placebo will be performed using a log-rank test stratified with standard of care to generate p-value for each comparison. Median time to hospitalization for respiratory ailments or death and corresponding 95% CI as well as proportion of subjects without the event at the 8- week interval will be summarized for each treatment arm using the Kaplan-Meier (KM) analysis. KM plot of time to hospitalization for respiratory ailments or death will also be presented by treatment. The hazard ratio and 95% CI will be calculated from a stratified Cox proportional hazards model that including standard of care as the strata.

Rate of mortality due to any cause, which is defined as the number of patients who died due to any cause, divided by the total study duration (years) summed over patients in that treatment arm and then multiplied by 100 to present in terms of per 100 patient years, will be analyzed similarly as the rate of hospitalization for respiratory ailments. In addition, overall survival which is defined as the time from start of study treatment to death due to any cause will be analyzed similarly as time to hospitalization for respiratory ailments. Any patient not known to have died at the time of analysis will be censored to the last known alive date.

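### SAP 7.5.2.4 defines death as an event for time to first IPF exacerbation or death, but its censoring sentence and two output labels leave death out

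*SAP*

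**What the plan says.** The heading of SAP 7.5.2.4 names a composite, and so does its definition: "Time to first IPF exacerbation or death is defined as the time from start of study treatment to first acute exacerbation of IPF", which goes on to include death. The test sentence agrees: "The analysis of time to first IPF exacerbation or death of each active treatment arm versus placebo will be performed using a log-rank test".

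Three other statements in the section do not agree:

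- Censoring: "Subjects who do not experience acute exacerbation of IPF will be censored to the last known alive date".
- Median: "Median time to first IPF exacerbation and corresponding 95% CI".
- Plot: "KM plot of time to first IPF exacerbation will also be presented by treatment".

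Section 7.5.2.5 handles the equivalent hospitalization endpoint differently. Its censoring rule is "Subjects who do not experience hospitalization for respiratory ailments and have not died will be censored to last known alive date". Its outputs are "Median time to hospitalization for respiratory ailments or death and corresponding 95% CI" and "KM plot of time to hospitalization for respiratory ailments or death will also be presented by treatment".

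The endpoint list in SAP 3.2 includes death. SAP Section 8 records that death was added to the protocol's exacerbation-only endpoint in order to avoid dependent censoring.

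**The concern.** The censoring sentence is the instruction from which the event indicator is programmed. It depends only on the absence of an exacerbation, so it and the definition classify a death without exacerbation in opposite ways. If the indicator is built from that sentence, the log-rank test, hazard ratio and Kaplan-Meier estimates describe exacerbation alone and treat death as ordinary censoring, which is what Section 8 set out to prevent. The Cox sentence and the 8-week event-free proportions name no endpoint, so they inherit the ambiguity.

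The rule also reaches beyond 7.5.2.4. Section 7.5.3 repeats all of 7.5.2 in the per-protocol population. Section 7.5.4 uses the endpoint for subgroup hazard ratios, which are withheld when there are fewer than 10 events across the two arms compared. That count depends on which sentence is followed.

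**Working it through.** **Text comparison.**

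| Element | 7.5.2.4 (exacerbation or death) | 7.5.2.5 (hospitalization or death) |
|---|---|---|
| Definition | includes death | includes death |
| Log-rank sentence | includes death | includes death |
| Censoring rule | no condition on death | requires that the subject has not died |
| Median label | omits death | includes death |
| Kaplan-Meier plot label | omits death | includes death |

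The transplant-or-death censoring rule in 7.5.2.5 likewise censors only patients with neither event. Of these three composites, only 7.5.2.4 lacks the condition.

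**Numerical illustration.** The SAP states no event count, hazard ratio or power for this endpoint, so there is no figure to reproduce. Only the 40 subjects per arm (SAP 2.3) and the visit days come from the documents. Every event input below is an assumption.

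*Event-free proportion.* Take 40 subjects, no other censoring, *e* exacerbations and *k* deaths without exacerbation, with e + k = 6 (15%).

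- Definition: (40 − 6)/40 = 85.0%.
- Literal rule: the product over exacerbations of (r − 1)/r, where r is the number at risk and deaths only reduce r. The lower limit has all deaths first and the upper limit has all deaths last.

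| e, k | Definition | Literal rule |
|---|---|---|
| 5, 1 | 85.0% | 34/39 = 87.2% to 35/40 = 87.5% |
| 4, 2 | 85.0% | 34/38 = 89.5% to 36/40 = 90.0% |
| 2, 4 | 85.0% | 34/36 = 94.4% to 38/40 = 95.0% |

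*Hazard ratio and event count.* Assume independent constant hazards, 15% of placebo subjects with a first event by Week 34, exacerbation hazard unchanged on active treatment and death hazard doubled. Let *d* be the share of placebo first events that are deaths.

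- Composite HR = (1 − d) × 1 + d × 2. Literal HR = 1.00, because only exacerbations count.
- Placebo first events = 6. Active first events = 40 × (1 − 0.85^HR).
- Exacerbations only: placebo 6 × (1 − d); active first events × (1 − d)/HR.

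| d | Composite HR | First events, both arms | Literal HR | Exacerbations only, both arms |
|---|---|---|---|---|
| 0.2 | 1.20 | 6 + 7.09 = 13.1 | 1.00 | 4.80 + 4.72 = 9.5 |
| 0.4 | 1.40 | 6 + 8.14 = 14.1 | 1.00 | 3.60 + 3.49 = 7.1 |
| 0.6 | 1.60 | 6 + 9.16 = 15.2 | 1.00 | 2.40 + 2.29 = 4.7 |

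Precision is poor. With SE(log HR) = √(1/E₁ + 1/E₀), where E₁ and E₀ are the event counts in the active and placebo arms, the d = 0.6 case gives √(1/9.16 + 1/6) = 0.525. The approximate 95% CI around 1.60 is then 0.57 to 4.48.

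*Lower event rates.* Assume instead yearly hazards of 0.05 to 0.10 for each component, with 80 subjects per comparison followed from Day 1 to Day 239 (238/365.25 = 0.652 years). Expected composite events are 80 × (1 − exp(−(sum of hazards) × 0.652)), which is about 5.0 to 9.8. With deaths censored, about 2.5 to 5.0 remain. The literal rule therefore drops one third to two thirds of the events.

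**The case against.** The strongest reply is that the SAP already settles the reading. The heading, definition, log-rank sentence, endpoint list and Section 8 all make death an event, so a careful programmer would follow them. It is also fair to say that a literal reading produces a conflict between sentences and not cleanly an exacerbation-only analysis, because the log-rank sentence names death. That limits the weight of the point. It does not remove the contradiction, because the outlying sentence is the operative censoring rule and it fits the protocol's exacerbation-only endpoint.

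Several points about size also stand:

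- The hazard-ratio contrast follows directly from assuming that deaths double and exacerbations do not change.
- Exacerbations are identified by the adverse event preferred term for IPF. A fatal event coded to that term would count under either rule, so the larger assumed death shares may be too high.
- At 15% events the median is not reached under either rule, so its label changes no estimate there.
- Most subgroup levels may fall below 10 events either way.

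The comparison with 7.5.2.5 should be confined to its time-to-event rules. The transplant-or-death rate in that section defines its numerator by transplantation alone, so it has an omission of its own.

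**Conclusion.** The concern holds. SAP 7.5.2.4 contradicts itself on whether a death without exacerbation is an event, and two of its output labels leave death out. Followed as written, the censoring sentence changes the estimand and undoes the change declared in Section 8.

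Under the assumed inputs, the event-free proportion in an arm of 40 would be overstated by about 2 to 10 percentage points, and one third to two thirds of composite events could be lost at the lower event rates. These figures illustrate a change of estimand. They do not estimate dependent-censoring bias, and with so few events no claim is made that the difference would be detectable.

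The impact is limited. The endpoint is secondary and untouched by any multiplicity procedure (SAP 7.1). Deaths are also counted in the mortality rate, overall survival, and the time-to-event analyses of hospitalization or death and transplantation or death. The text should be corrected, but the primary safety endpoints are not affected.

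**What to change.** In SAP 7.5.2.4:

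1. Add the condition *and have not died* to the censoring sentence, so that only subjects with neither an exacerbation nor death are censored at the last known alive date.
2. Label the median and the Kaplan-Meier plot as time to first IPF exacerbation or death.

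In the same edit, Section 8 should say exacerbation *or* death; it now says *and*, unlike 3.2 and 7.5.2.4. The per-protocol repeat in 7.5.3 and the subgroup hazard ratios and 10-event count in 7.5.4 then follow the corrected rule without further change.

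The cost is wording only: no new data, no added analysis and no change to the intended endpoint. The correction should precede programming and unblinding, so that the event definition is not settled with results in view.

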**CONFIDENTIAL**

## Statistical Analysis Plan

Sponsor Name: Nitto Denko Corporation  
Sponsor Protocol ID: ND-L02-s0201-005

The rate of acute IPF exacerbation, which is defined as the number of patients with any acute IPF exacerbation divided by the total study duration (years) summed over patients in that treatment arm and then multiplied by 100 to present in terms of per 100 patient years, will be summarized by treatment arm. Tests of differences in rates between treatment arms will be assessed using chi-squared tests ( $\chi^2$ ) at the 2-sided, 0.05 level of significance. Corresponding exact 95% CIs of study treatment proportions and respective active ND-L02-s0201 differences from placebo will be estimated.

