### 3.2 Secondary Endpoints

#### Biological Activity

## Statistical Analysis Plan

Sponsor Name: Nitto Denko Corporation  
Sponsor Protocol ID: ND-L02-s0201-005

- Rate of decline in FVC from baseline to Visit 14 (Day 169) (measured in L and % of predicted over unit time)
- Absolute and relative change in FVC (L and % of predicted) at Visit 14 (Day 169) as compared with baseline
- Proportion of subjects with an FVC response (L and % of predicted) defined as either having improvement or a decline by 0% to  $\leq 5\%$ ,  $> 5\%$  to  $\leq 10\%$ , and by  $> 10\%$  at Visit 14 (Day 169)
- Change in DLCO (mL/min/mmHg) and DLCO (mL/min/mmHg) corrected for hemoglobin at Visit 14 (Day 169)
- Changes of ILA as measured by HRCT (i.e., change in parenchymal feature [Baseline to Visit 14 (Day 169)]), as determined by qualitative assessment (central radiologist) and quantitative analysis (Quantitative Lung Fibrosis – QLF analysis)
- Time to first acute IPF exacerbation (i.e., an unexplained worsening of dyspnea, evidence of hypoxemia as defined by worsened or severely impaired gas exchange, new radiographic alveolar infiltrates, and an absence of an alternative explanation such as infection, pulmonary embolism, pneumothorax, or heart failure [Raghu et al, 2011]) or death
- Rate of hospitalization for respiratory ailments and time to first hospitalization for respiratory ailments or death
- Rate of mortality due to all causes and overall survival
- Rate of deterioration of IPF resulting in lung transplantation (up to 12 weeks after the end of study treatment) or death and time to deterioration of IPF resulting in lung transplantation (up to 12 weeks after the end of study treatment) or death

[REDACTED]

- [REDACTED]
- [REDACTED]
- [REDACTED]

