Rate of deterioration of IPF resulting in lung transplantation (up to 12 weeks after the end of study treatment) or death, which is defined as the number of patients with

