## Statistical Analysis Plan

Sponsor Name: Nitto Denko Corporation  
Sponsor Protocol ID: ND-L02-s0201-005

any deterioration of IPF resulting in lung transplantation divided by the total study duration (years) summed over patients in that treatment arm and then multiplied by 100 to present in terms of per 100 patient years, will be analyzed similarly as the rate of hospitalization for respiratory ailments. In addition, time to deterioration of IPF resulting in lung transplantation or death defined as the time from start of study treatment to deterioration of IPF resulting in lung transplantation (up to 12 weeks after the end of study treatment) or death will be analyzed similarly as time to hospitalization for respiratory ailments. Any patient not known to have IPF resulting in lung transplantation (up to 12 weeks after the end of study treatment) or death at the time of analysis will be censored to 12 weeks after the end of study treatment or the last known alive date, whichever is earlier.

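### SAP 7.5.2.4 and 7.5.2.5 report rates per 100 patient-years but specify intervals for crude proportions, and the transplantation-or-death rate leaves deaths out of its numerator

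*SAP*

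**What the plan says.** SAP 7.5.2.4 defines the exacerbation rate as the number of patients with at least one event "divided by the total study duration (years) summed over patients in that treatment arm and then multiplied by 100". It then states "Tests of differences in rates between treatment arms will be assessed using chi-squared tests", at the two-sided 0.05 level, and adds "Corresponding exact 95% CIs of study treatment proportions" and of the differences of each active arm from placebo.

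SAP 7.5.2.5 defines the respiratory hospitalization rate in the same way and repeats the method: "Tests of differences in event rate will be assessed using chi-squared tests", again with exact intervals for proportions. Two further rates follow by cross-reference to hospitalization. One is "Rate of mortality due to any cause, which is defined as the number of patients who died due to any cause" over the same patient-year denominator. The other is introduced as "Rate of deterioration of IPF resulting in lung transplantation (up to 12 weeks after the end of study treatment) or death", but its numerator is patients with "any deterioration of IPF resulting in lung transplantation divided by the total study duration (years) summed over patients in that treatment arm".

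SAP 3.2 lists the hospitalization, mortality and transplantation-or-death rates as secondary endpoints, each paired with a time-to-event measure, for example "Rate of hospitalization for respiratory ailments and time to first hospitalization for respiratory ailments or death". For exacerbation it lists only the time to first event or death, so the exacerbation rate in 7.5.2.4 is an addition. Each endpoint also has a stratified log-rank test, a Kaplan-Meier summary and a stratified Cox model.

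**The concern.** The estimate has patient-years in its denominator. The interval has the number of subjects in its denominator, and the test is most naturally read as having it too. No interval for a rate or rate ratio, and no person-time test, appears in the visible text. A clinical study report that follows the SAP would then carry rates with no interval of their own, together with intervals that could be taken for theirs. If follow-up differed between arms, the proportion test would lean toward the arm observed for less time.

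The second matter is a contradiction within one definition. The rate is named for transplantation or death, and its time-to-event companion includes death, but the written numerator does not. A programmer following the text would report a listed secondary endpoint without its deaths.

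**Working it through.** **Inputs from the documents.** About 40 subjects per arm (SAP 2.3). The last scheduled visit is Week 34, Day 239 (SAP Appendix 2). Tests are two-sided at 0.05 without multiplicity adjustment (SAP 7.1). Neither document visibly states an event rate, a dropout rate or power, so there is no plan figure to reproduce. All event counts, hazards and dropout patterns below are assumptions.

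**1. Interval, equal follow-up.** Patient-years per arm = 40 x 34/52 = 26.15.

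| Assumed events | Rate per 100 PY | Exact Poisson CI of the rate | Proportion | Exact (Clopper-Pearson) CI of the proportion |
|---|---|---|---|---|
| 8 | 8/26.15 = 30.6 | 13.2 to 60.3 | 8/40 = 20.0% | 9.1% to 35.6% |
| 4 | 4/26.15 = 15.3 | 4.2 to 39.2 | 4/40 = 10.0% | 2.8% to 23.7% |

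The Poisson limits for a count x are half the 2.5% chi-squared quantile on 2x degrees of freedom and half the 97.5% quantile on 2x + 2, divided by patient-years. For x = 8 these are 3.454/26.15 and 15.763/26.15. Most of the gap is the unit. Dividing the proportion limits by 34/52 gives 9.05/0.654 = 13.8 and 35.65/0.654 = 54.5 per 100 patient-years. That conversion is simple only when everyone has the same follow-up.

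**2. Test, unequal follow-up.** Assume equal true hazards L, and a share f of an arm observed to week 14 only. The event probability is (1 - f)(1 - exp(-L x 34/52)) + f(1 - exp(-L x 14/52)). At 0.2/year the two pieces are 12.26% and 5.24%, so f = 15% gives 0.85 x 12.26 + 0.15 x 5.24 = 11.2%. Rejection probability comes from full enumeration of two binomials with n = 40 each.

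| Hazard per year | Share ending at week 14 | Event probabilities | Size, uncorrected | Size, continuity-corrected |
|---|---|---|---|---|
| 0.2 | 0 vs 0 | 12.3% both | 5.6% | 1.6% |
| 0.2 | 15% vs 25% | 11.2% vs 10.5% | 5.9% | 1.5% |
| 0.2 | 0 vs 30% | 12.3% vs 10.2% | 6.8% | 2.0% |
| 0.5 | 0 vs 0 | 27.9% both | 4.9% | 2.7% |
| 0.5 | 15% vs 25% | 25.6% vs 24.1% | 5.3% | 2.8% |
| 0.5 | 0 vs 30% | 27.9% vs 23.3% | 7.5% | 4.3% |

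At 0.1/year the uncorrected size is 4.9% to 5.5% across the same three patterns. The one-sided error favouring the shorter-followed arm, uncorrected, rises from 2.8% and 2.5% (equal follow-up, 0.2 and 0.5/year) to 3.6% and 3.6%, then to 5.4% and 6.7%.

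**3. Transplantation-or-death numerator.** Assume one transplantation and two deaths in different subjects, in 26.15 patient-years. As written the rate is 1/26.15 = 3.8 per 100 patient-years. As named it is 3/26.15 = 11.5.

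**4. Time after the first event.** Each patient counts once, but total study duration continues past the first event. With full follow-up T = 34/52 this multiplies a non-fatal first-event rate by (1 - exp(-LT))/(LT) = 0.968, 0.937 and 0.853 at 0.1, 0.2 and 0.5/year.

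**The case against.** The strongest reply is that the SAP says openly that its intervals are for proportions. No table shell is visible, so the output may show n (%) with that interval and the rate elsewhere. This stands as far as layout goes: that a rate will be printed directly beside a proportion interval is an inference. It does not supply the missing interval for the rate, and the SAP itself calls the proportion test a test of differences in rates.

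A reader might infer that the p-values are invalid even with equal follow-up. They are not. Equal rates over equal follow-up imply equal proportions, so chi-squared tests the same null, and its size above is 4.9% to 5.6%.

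A reader might also infer serious error inflation. The documents do not support that. The inflation needs unequal follow-up and an uncorrected test, and the SAP does not say whether a continuity correction applies. With one, size stays at or below 4.3% in every scenario examined. Larger figures, about 10% to 12%, appear only with assumed mean follow-up of 0.61 versus 0.42 years. Protocol 8.4.1 makes withdrawal of consent the only intended reason for leaving the study and asks for outcome follow-up after treatment stops. Required adverse event reporting does end 12 weeks after the last dose (protocol 14.5), so some imbalance remains possible.

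Nor is time-based inference absent. Stratified log-rank and Cox analyses cover mortality and the named transplantation-or-death endpoint directly. For exacerbation and hospitalization they cover composites with death only, for exacerbation by a stated choice (SAP 8). Counting patients over total study duration is a defined convention applied alike in every arm.

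**Conclusion.** The interval mismatch holds as written and needs no dropout assumption. The specified exact intervals estimate proportions, and the rates per 100 patient-years have none of their own. The illustrative sizes rest on assumed counts of 8 and 4.

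The test is a lesser matter. It is sound for no difference under equal follow-up and modestly liberal under assumed imbalance if uncorrected. That it is run on patient counts out of n is the natural reading, given the accompanying proportion intervals, but the SAP does not write out the table.

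The numerator contradiction in 7.5.2.5 is plain and affects a listed secondary endpoint. As written, that rate comparison concerns transplantation alone, while its time-to-event companion includes death.

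Priority is minor. These are unadjusted secondary analyses in a trial whose primary endpoints are safety, and the main time-based inference lies in the log-rank and Cox analyses.

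**What to change.** In SAP 7.5.2.4 and 7.5.2.5:

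1. Label the chi-squared test and its exact intervals as comparing the crude proportion of subjects with an event, and show them with n/N. State whether a continuity correction is used.
2. Give each rate per 100 patient-years its own exact Poisson 95% CI on the patient-years used. Because each patient counts once, this interval is somewhat wide (13.2 to 60.3 against the rescaled 13.8 to 54.5 above).
3. Make the numerator of the transplantation-or-death rate include deaths, to agree with SAP 3.2, the rate's own name and its time-to-event companion.

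Optional: stop person-time at the first event, and add a rate ratio of each active arm versus placebo with a mid-P or Poisson score interval. This assumes a constant rate, and in simulations under the same kind of assumptions the mid-P test was conservative when events were few (size 2.1% to 3.1% at 0.1/year).

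The cost is a few sentences in the SAP and one more procedure call on data already collected. No change to data collection is needed.
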